2.2 Background

Infertility is defined as not being able to get pregnant after one year of unprotected sex. About 6% of married and overall 12% of women ages 15 to 44 have infertility issues. Infertility issues can be of male or female origin. According to the CDC, in 35% of the infertility cases a male factor was found along with a female factor and in 8% of the cases the only identifiable cause was a male factor. Fertility is affected by multiple factors, one of which is the female's age. For this reason it is recommended that people anatomically female under the age of 35 seek help after one year of trying to conceive while those over the age of 35 should seek help after 6 months. One of the first options available is artificial insemination.

The first documented case of artificial insemination was done in the 1770s by John Hunger in London (Obmelet & Robays 2015). Subsequently J. Mario Sims reported his findings in the mid-1880s. Sims describes 55 inseminations. Unfortunately since he believed ovulation occurred during meneses, only one pregnancy was reported (Obmelet & Robays 2015). Research has come a long way since the early 18th century. Artificial insemination is now a much more frequent occurrence. Initially used by couples with male infertility (low sperm count and inherited Y-chromosome disease), later for couples with physiological and psychological dysfunction, such as retrograde ejaculation, vaginismus, hypospadias and impotence, and now

is very commonly used by people with no male partner (both single and those in lesbian relationships).

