Analysis: Descriptive statistics will be used to analyze perceived safety. Qualitative analysis will be used on any comments made related to safety. Rates of vaginal infections will be analyzed using descriptive statistics.

Secondary Hypothesis 5: The majority of participants indicate they have little to no safety concerns related to using the Mosie Kit. Alternative hypothesis is the majority of participants will be very concerned or extremely concerned about the safety of using the Mosie Kit.

Analysis: Descriptive statistics of self-reported level of concern. Additionally, safety measures such as hand washing, disposing of the syringe after use, and reading the instructions will be examined using descriptive statistics.

Tertiary Hypothesis 1: There will be higher pregnancy rates when using the Mosie Kit when the source of infertility is male-based than when it is female-based. The alternative hypothesis is there will be lower pregnancy rates when using the Mosie Kit when the source of infertility is male-based than when it is female-based.

Analysis: In addition to the descriptive statistics a t-test will be run to examine this hypothesis.

Tertiary Hypothesis 2: There is a difference in pregnancy rates of people with known fertility issues depending on the source of their infertility. Specifically, the following sources of infertility will be examined if sufficient data is available.

- o PCOS
- Endometriosis
- Low AMH or low ovarian reserve
- Low sperm count
- Sperm motility issues
- Unexplained infertility
- Erectile dysfunction
- Performance issues or sexual anxiety, or inability to orgasm with partner.

Page 27

- Vaginismus or vulvodynia
- Tilted uterus
- Multiple uterus/cervix
- Loss of a fallopian tube

The alternative hypothesis is that there will be no difference in the fertility rates associated with different sources of infertility.

Analysis: Descriptive statistics, t-test, correlations and multiple ANOVAs will be used to examine this hypothesis.

Tertiary Hypothesis 3: There will be a difference between individuals who perform 2 insemination instances as described in the instructions and those that follow a different schedule or dosage number. The alternate hypothesis is that there will be no difference between the individuals that perform the minimum 2 insemination instances and those that follow difference dosage schedule.

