9.4 Statistical Analyses

9.4.1 General Approach

Statistical analysis will commence with descriptive statistics for each survey question and plotting of the individual data into scatter plots to understand the data distribution. If any information suggests corrective procedures should be employed, the appropriate transformation or non-parametric test will be used.

Categorical values will be reported using descriptive statistics and frequency of occurrence. Key categorical values will also be converted into a percentage of total responses in order to allow an understanding of the prevalence of the response in the sample. For continuous variables, the means with standard deviations, median and range will be reported.

Qualitative data is only expected as a response to two questions, an open ended safety question and an additional comments question. The responses will be evaluated and categorized. Then the frequency of each category will be provided.

For inferential tests such as t-tests and ANOVAs, a p-value of 0.05 and a confidence interval of 95% will be used for statistical significance. The type of hypothesis will determine whether the specific tests will be one-tailed or two-tailed. Hypothesis seeking to understand whether there is or is not a difference will use a two-tailed test while those seeking a greater than or less than relationship will use a one-tailed test. Correlations among some of the variables will also be examined as appropriate.

Statistical analysis process for each hypothesis has already been described in section 9.1. No baseline analysis is used for cross-sectional studies. No interim analyses are planned for cross-sectional one survey studies.

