Appendix A: Online Survey Tool and Consent Form (Google Form)

This section shows what the Google Form will look like to the study participant. These are the questions the participant will be asked.

The first page of the study contains the consent form and the question that confirms the participant's agreement to participate.

There is skip logic for certain sections. For example, if the participant selects one cycle of using Mosie, the information related to cycles 2-6 will be skipped. If the participant selects that she is pregnant the questions related to the pregnancy will be asked, otherwise they will be skipped. If a donor was used, the questions related to producing a sperm sample will be skipped.

Note: Final language and questions might be tweaked or revised at any time to increase clarity.

MOSIE-001 © 2020 Mosie Baby Page 38

[figure not shown]
This is the inclusion/exclusion form.

If Participant selected to not participate in the study, he/she will see this screen next. If the participant said he/she is not 18 or older or has not used Mosie this screen will be displayed.

[figure not shown]

Qualifying participants will continue the survey on this page.

[figure not shown]

[figure not shown]
	ch of these diagnoses or issues do you believe are contributing to your rtility? *
	Not applicable
	PCOS
	Endometriosis
	Low AMH or low ovarian reserve
	Low Sperm count
	Sperm motility issues
	Erectile Dysfunction
	Performance issues or sexual anxiety, or inability to orgasm with partner
	Vaginismus or vulvodynia
	Tilted Uterus
	Multiple uterus/cervix
	Unexplained infertility
	Have only one functioning fallopian tube
П	Other:

[figure not shown]
No other method	is attempted			
Male/Female into	ercourse			
IVI or syringe oth	ner than Mosie			
IUI				
Femara				
Clomid				
IVF				
Cervical Cap				
Other:				
	None	1	2	3 or more
How many pregnancies have you had?	0	0	0	0
pregnancies	0	0	0	0
pregnancies have you had? How many live births have you had? How many pregnancies have you had that were	0	0	0	0
pregnancies have you had? How many live births have you had? How many pregnancies have you had	0	0	0	0

[figure not shown]

[figure not shown]
	0	1	2	3+
24-48 hours prior to ovulation	0	0	0	0
within 24 hours of ovulation	0	0	0	0
24-48 hours after ovulation	0	0	0	0
48+ hours after ovulation	0	0	0	0
Did you use Mosie fo Yes No	or another cy	cle?		

[figure not shown]

[figure not shown]

[figure not shown]

[figure not shown]

Mosie Kit Survey

* Required

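### Tertiary Hypotheses 1 and 2 compare infertility sources that probably overlap, and the plan has no rule for respondents with both factors or several causes

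*Combined protocol and SAP*

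**What the plan says.** Tertiary Hypothesis 1 in Section 9.1 reads: "There will be higher pregnancy rates when using the Mosie Kit when the source of infertility is male-based than when it is female-based". Its analysis is: "In addition to the descriptive statistics a t-test will be run to examine this hypothesis". Section 9.4.1 sets the level ("For inferential tests such as t-tests and ANOVAs, a p-value of 0.05 and a confidence interval of 95% will be used for statistical significance") and adds that "those seeking a greater than or less than relationship will use a one-tailed test", so this directional hypothesis would be tested one-tailed at 0.05.

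Tertiary Hypothesis 2 names twelve sources of infertility, to be examined where the data suffice. Its analysis is: "Descriptive statistics, t-test, correlations and multiple ANOVAs will be used to examine this hypothesis".

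On overlap, Section 2.2 reports that "in 35% of the infertility cases a male factor was found along with a female factor" and that "in 8% of the cases the only identifiable cause was a male factor". The Appendix A survey asks which "of these diagnoses or issues do you believe are contributing to your" infertility. It offers the twelve causes, a not-applicable option and Other.

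Two further places bear on this. Section 9.4.2 makes male or female infertility a subgroup factor for all endpoints. Section 9.4.3 plans exploratory modelling of pregnancy on several variables, among them source of infertility, age and number of cycles.

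No section defines male-based or female-based, assigns the twelve causes to a side, or says how a respondent with more than one cause is classified.

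**The concern.** A two-group t-test, as ordinarily run, puts each respondent in one group. If many respondents have both a male and a female factor, the result depends on where they are put. Counting them on both sides makes the groups share people and pulls the two rates together. Putting them all on one side mixes two kinds of couple in that group. Leaving them out, or giving them their own category, dilutes nothing. The plan leaves all of these open, so the choice could be made after the data are seen.

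The rationale given for the tertiary objective in Section 3 is that success is likelier when the woman has no fertility issue and semen reaches the cervix. That describes male-only infertility. A male-based group made up largely of couples who also have a female factor would test something else.

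For Tertiary Hypothesis 2, a comparison of people with and without one cause picks up the effect of whatever other causes tend to accompany it.

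**Working it through.** **The plan's own precision figure.** Section 9.2 gives ±4.4% for 500 surveys and ±5% for 384. Using 1.96 × √(0.25/n), n = 500 gives 4.38% and n = 384 gives 5.00%, so both reproduce. They concern a single overall proportion. No sample size or power is given for Tertiary Hypotheses 1 or 2.

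**Overlap implied by Section 2.2.** Male factor with female factor is 35% and male factor alone is 8%, so any male factor is 43%. Of these, 35/43 = 81.4% also have a female factor and 8/43 = 18.6% do not.

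**Share of the true difference that stays visible.** Let d be the pregnancy rate in male-only minus that in female-only cases. Let q place the both-factor rate between them (q = 0 at the female-only rate, q = 1 at the male-only rate). Let F be the female-only share in percent. The documents do not give F. I take 20 to 57, where 57 = 100 − 43 is the maximum. Then:

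- any-male group = female-only rate + d × (8 + 35q)/43
- any-female group = female-only rate + d × 35q/(35 + F)

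| Rule for both-factor respondents | q = 0 | q = 0.5 | q = 1 |
|---|---|---|---|
| Counted on both sides | 18.6% | 27.5%–40.3% | 36.4%–62.0% |
| Male group, against female only | 18.6% | 59.3% | 100% |
| Female group, against male only | 100% | 68.2%–81.0% | 36.4%–62.0% |
| Own category or excluded | 100% | 100% | 100% |

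Ranges within a cell run from F = 20 to F = 57. The share hidden is 100% minus the entry: 0% to 81% across all rules, and 38% to 81% when both-factor respondents count on both sides. A both-factor rate outside the interval between the two single-factor rates was not examined.

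**The worst case in points.** Assume male-only couples conceive at 40% and all couples with a female factor at 20%. With both-factor couples in the male group, its rate is (8 × 0.40 + 35 × 0.20)/43 = 23.7%. The comparison shows 23.7 − 20 = 3.7 points in place of 20. The 40% and 20% are illustrative; the retained share of 18.6% is 8/43 and does not depend on them.

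**Illustrative power.** Assume 300 respondents with a cause, 30% pregnant in male-only cases, 15% in all others, F = 57, one-sided 0.05. Power is Φ[(difference − 1.645 × SE₀)/SE₁], where SE₀ is the pooled and SE₁ the unpooled standard error.

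- Both-factor in the male group: 129 against 171 respondents, 17.8% against 15%, power 16%.
- Same group sizes without dilution: 30% against 15%, power 93%.
- Male only against female only: 24 against 171 respondents, 30% against 15%, power 56%.

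In this worst-case setting, exclusive groups gain power even though the male-only group is small.

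**The case against.** Several points on the other side stand.

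- The 35% and 8% describe infertility cases in general. The respondents are self-selected kit buyers, some single or in LGBTQ relationships, reporting what they believe contributes. The figures show that overlap is to be expected, not how large it will be.
- That several causes can be selected is inferred from the plural wording. The ovulation item in Appendix A carries an explicit instruction to select all that apply; the surviving text of the cause item does not, and that page is damaged in extraction. Multi-select is likely, not certain.
- Multiple ANOVAs may mean one present/absent comparison per cause. Each person then appears once per test and independence is not broken. What remains is confounding by co-occurring causes.
- The exploratory model in Section 9.4.3 comes close to a remedy. It gives no coding for several causes, however, and is not the stated test for either hypothesis.
- The absence of a side for unexplained infertility is not in itself an error. Tertiary Hypothesis 2 lists it as its own source, and Tertiary Hypothesis 1 does not claim to include it.

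A reader might infer that the plan will count both-factor couples twice or allocate them arbitrarily, so that most of the difference is bound to disappear. The documents do not support that: Section 9.1 states no rule, and excluding these couples is as compatible with it as including them. Nor would dilution refute a true hypothesis; it would leave it without support.

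**Conclusion.** The point holds as a missing classification rule with a potentially large effect. Overlap is expected on the protocol's own background figures, and the stated tests give no place to respondents with both factors or several causes. Between 0% and 81% of a true male-only versus female-only difference could be hidden, for both-factor rates between the two single-factor rates and an assumed female-only share of 20% to 57%.

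The fall from 20 points to 3.7 is the worst case in that range. It requires both-factor couples to be classed as male-based, to conceive at the female-only rate, and to occur among respondents in the background 8:35 ratio.

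The consequences are that a true Tertiary Hypothesis 1 may go unsupported and that single-cause results under Tertiary Hypothesis 2 cannot be attributed to one cause. A reader might extend this to the main results, but the primary hypothesis tests do not use the male/female split. Section 9.4.2 does carry the undefined split into subgroup analyses of all endpoints, so the same definition should serve there.

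**What to change.** **Tertiary Hypothesis 1.** Before analysis, map each listed cause to male, female or unclassified. Treat unexplained infertility, the performance, sexual-anxiety or orgasm item, and Other as unclassified unless the sponsor states otherwise. Form four exclusive groups: male only, female only, both, and unexplained/unclassified. State how a respondent with one classified and one unclassified cause is assigned. Test male only against female only, and report the both-factor group separately.

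**Tertiary Hypothesis 2.** Make one logistic model of pregnancy the stated analysis, with a yes/no indicator per cause plus age and cycles used, building on the model in Section 9.4.3. Use the existing data-sufficiency condition to say when a sparse cause is pooled or omitted, or when a penalised fit is used. That rule is needed: twelve indicators plus age and cycles are about 14 parameters. If 10% to 20% of 384 to 500 respondents are pregnant (an assumption), there are 38 to 100 events, or about 2.7 to 7 per parameter, and fewer if only people with fertility issues enter.

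**Cost.** Wording in Section 9.1 only; causes, age and cycles are already collected. The male-only group is smaller, so its interval is wider, and rare causes will not be estimated separately.

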9.3 Populations for Analyses

The population to be analyzed include any one using the Mosie Kit in the full 2-8 months prior to study commencement. Respondents can be male or female. Overall the data will be analyzed as a whole and stratified by sex (having ovaries and a uterus as indication of being a female), age and type of relationship.

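### Tertiary Hypothesis 1 compares male-based with female-based infertility, but one survey option does not say which partner has the problem, so those users must be dropped or coded by assumption

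*Combined protocol and SAP*

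**What the plan says.** Section 9.1 states Tertiary Hypothesis 1 as "higher pregnancy rates when using the Mosie Kit when the source of infertility is male-based than when it is female-based". The analysis is one line: "In addition to the descriptive statistics a t-test will be run to examine this hypothesis". Section 9.4.1 sets the threshold ("a p-value of 0.05 and a confidence interval of 95% will be used for statistical significance") and the direction ("those seeking a greater than or less than relationship will use a one-tailed test"), which makes this test one-tailed at 0.05. I found no section that says which sources count as male-based and which as female-based. Section 9.4.2 uses a male/female infertility split again for subgroups, also without a definition.

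The data come from a diagnosis item in Appendix A. Its stem is partly cut off; the legible part reads "ch of these diagnoses or issues do you believe are contributing to your", and the rest refers to infertility. One answer is "Performance issues or sexual anxiety, or inability to orgasm with partner". Erectile dysfunction, and vaginismus or vulvodynia, are separate answers. "Unexplained infertility" and a free-text Other are also offered.

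Section 9.3 says "Respondents can be male or female". Section 4.3 rules out any follow-up, and section 10.1.9.1 says no outside records will be joined to the survey data.

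**The concern.** The comparison needs each included user to have a source that belongs to one partner. Low sperm count or endometriosis does this by its nature. The performance, anxiety or orgasm option does not, because it can describe the person providing sperm or the person being inseminated. The respondent's own sex does not settle it, since either partner may answer and the item asks about contributing issues, not about who has them.

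Once the anonymous answers are in, the information cannot be recovered. The analyst can exclude these users or choose a side for them, and the plan does not say which. If their pregnancy rate is unlike the others, the side that receives them moves towards that rate, and the choice could be made after the results are visible. What is at stake is a statement about couples with a male-based source in a study whose aggregate results are meant for publication and possibly marketing (section 10.1.3).

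**Working it through.** **The plan's own figure.** Section 9.2 gives a precision for a single proportion only. Half-width = 1.96 × √(0.25/n): n = 500 gives 4.38 points (stated 4.4), and n = 384 gives 5.00 points (stated 5). Both reproduce. Neither bears on Tertiary Hypothesis 1, for which the plan gives no group sizes or rates. The group sizes and rates below are therefore assumptions.

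**Method.** For a yes/no outcome in samples of this size, the t-test is close to a pooled two-proportion z-test. With d = male rate − female rate and p̄ the pooled rate, SE = √[p̄(1 − p̄)(1/n₁ + 1/n₂)], z = d/SE, and one-sided p = 1 − Φ(z).

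**Main example (assumed).** 80 male-based users at 25% (20 pregnancies), 150 female-based at 20% (30 pregnancies), 40 disputed at 45% (18 pregnancies).

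| Disputed group | Male | Female | d (points) | SE | z | one-sided p |
|---|---|---|---|---|---|---|
| coded male | 38/120 = 31.7% | 30/150 = 20.0% | +11.7 | 0.0532 | 2.19 | 0.014 |
| coded female | 20/80 = 25.0% | 48/190 = 25.3% | −0.3 | 0.0579 | −0.05 | 0.52 |
| excluded | 20/80 = 25.0% | 30/150 = 20.0% | +5.0 | 0.0571 | 0.88 | 0.19 |

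The change in significance is clear. The change of sign is marginal.

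**When the sign changes.** Coding the group as female makes d negative only if n(disputed)/n(female) exceeds (male rate − female rate)/(disputed rate − male rate). In the main example this is 0.05/0.20 = 0.25, or 37.5 of 150 users, and 40 is just above it. With the female rate at 20%:

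| Male advantage | Disputed rate 43% | Disputed rate 69% |
|---|---|---|
| 2 points | 0.02/0.21 = 10% of the female group | 0.02/0.47 = 4% |
| 5 points | 0.05/0.18 = 28% | 0.05/0.44 = 11% |
| 10 points | 0.10/0.13 = 77% | 0.10/0.39 = 26% |

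The 43% and 69% are borrowed from the study of unconsummated marriages cited in section 2.2, as illustrations only. If the disputed rate lies between the other two, the sign cannot change: pooling moves one group's rate towards the other's but not past it.

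**Cases with less or no effect (assumed).**
- Main example with 20 disputed users: +9.0 points (p = 0.0503) coded male, +2.1 points (p = 0.36) coded female. There is no sign change, and neither result is strictly below 0.05.
- 100 male-based at 25%, 150 female-based at 20%, 25 disputed at 43%: +8.6 (p = 0.048) against +1.7 (p = 0.37). Significance changes, the sign does not.
- 100 at 30%, 150 at 20%, 50 disputed at 25%: +8.3 (p = 0.046) against +8.75 (p = 0.048). The conclusion does not change.

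**The case against.** Nothing in the plan requires every source to be placed on one side. The list of sources belongs to Tertiary Hypothesis 2, where each is examined only if there are enough data. Users who fit neither group can be left out, and in the main example that simply returns the 5-point difference built into it. Unexplained infertility is neither male- nor female-based on its face, so leaving it out is the natural reading. This stands, and the point is confined to the one option that could be attributed if the survey asked.

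A reader might infer that these users have the highest success rate, because section 3 argues that the kit helps where the problem is erectile dysfunction and section 2.2 cites 69%, 43% and 25% conception by age group. The documents do not support that step. The cited couples had vaginismus, erectile dysfunction or premature ejaculation. Erectile dysfunction and vaginismus have their own boxes, and no rate is given for users who tick only the disputed one. The lowest cited rate, 25%, is also close to what is assumed for everyone else.

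Several screens in Appendix A could not be read, including those next to this item, so a question on whose problem it is may exist. That limits the claim to the legible text. Even then, section 9.1 would need to say how the answer is used.

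Mixed answers may matter more: section 2.2 puts a male factor found together with a female factor at 35% of cases. That is fair. Restricting the test to users with one attributable side deals with both.

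**Conclusion.** The point holds in limited form. In the legible survey, one option cannot be attributed to a partner, the design prevents attribution later, and Tertiary Hypothesis 1 depends on attribution. Coding by assumption can move the one-sided p-value from 0.014 to 0.52 under the assumed inputs of the main example, and in some cases it turns the sign.

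A reader might conclude that the coding will reverse the result. The documents do not show that. They give no counts or rates, and a reversal needs a disputed group that is large relative to the group it joins and whose rate lies outside the range of the other two. With small groups or intermediate rates the effect is slight or absent. The hypothesis is tertiary, and no overall primary or secondary result depends on it. The case for acting is that the information is cheap to collect now and lost afterwards.

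**What to change.** Split the option in Appendix A into two, one for the person providing sperm and one for the person being inseminated, unless a screen that could not be read already asks this. Appendix A allows questions to be revised for clarity, so the change is within the plan's own terms. Add a sentence to section 9.1 saying that Tertiary Hypothesis 1 uses only users whose reported sources are all attributable to the same partner. Unexplained, unattributable Other and mixed answers then stay out of both groups.

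If the form is already fixed, exclude the unsplit option from the main comparison and report the result with it coded each way as sensitivity analyses.

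The cost is one more survey option, one sentence in section 9.1 and a slightly smaller sample for this hypothesis.
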